### 6.5.4 Non-Quantifiable Laboratory Data

Not applicable.

### 6.5.5 Implausible Participant Reported Outcomes

Values measured and reported by the participant directly (e.g., via the electronic or paper diary) are not corrected in a reconciliation process. In cases where the reported values are clearly biologically implausible, the reported values and associated toxicity grades are set to missing and excluded from analysis. These reported values are included in listings.

Example: Body (oral) temperatures less than  $\leq 33^{\circ}\text{C}$  or  $\geq 42^{\circ}\text{C}$ .

## 6.6 Adjustment for Covariates

Beyond the inclusion of site in the immunogenicity ANOVA models described in Section 6.1, no further adjustment for covariates is performed. Immunogenicity analyses are conducted for both age strata pooled as well as by separate age strata.

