Geometric mean titers: Geometric mean titers will be derived from a linear analysis of variance (ANOVA) model with \log_{10} -transformed CHIKV SNA titers as the dependent variable and treatment group and study site as fixed effects. The adjusted least square means and their two-sided 95% CIs calculated based on the ANOVA model will be back transformed and reported as the PXVX0317 and placebo group GMT values at Day 15, Day 22, and Day 183. Significance testing will be carried out at a two-sided significance level of 0.05 using both age strata combined.

Geometric mean fold increase: Geometric mean fold increase in CHIKV SNA titers from Day 1 to Day 15, Day 22, and Day 183 will be reported for PXVX0317 and placebo groups.

Four-fold rise over baseline in CHIKV SNA titer: Proportions (percentages) of participants in PXVX0317 and placebo groups with a CHIKV SNA titer of at least 4-fold rise over baseline at Day 15, Day 22, and Day 183 will be summarized with two-sided 95% CIs based on the Wilson score method.

Safety endpoints: The safety of PXVX0317 in adults ≥ 65 years of age will be evaluated using solicited AEs occurring from IP administration on Day 1 until Day 8, unsolicited AEs through Day 29, MAAEs, AESI, and SAEs through Day 183 End of Study Visit, and vital signs. Solicited AEs include local (pain, redness, and swelling) and systemic reactions (fever, chills, fatigue, headache, myalgia, arthralgia, and nausea).

Sample Size Considerations: Based on the data from the phase 2 study (protocol PXVX-CV-317-001), the seroresponse rate for PXVX0317 vaccine is expected to be approximately █ vs <5% for the placebo participants. With an assumed 10% rate of nonevaluable participants, the power to show superiority over placebo with 180 PXVX0317 vaccine and 180 placebo evaluable participants is >99.9% for the combined age groups.

The difference in seroresponse rate between PXVX0317 and placebo groups that is considered clinically relevant is █. With 180 PXVX0317-treated participants and a target seroresponse rate of █ vs a rate of 5% for placebo, the width of a two-sided 95% CI would be $\pm 5.4\%$. If the target PXVX0317 seroresponse is █, the width would be $\pm 6.9\%$. Therefore, the difference in seroresponse rates must be above █ for the lower bound of the 95% CI for the difference to be █.

Analysis Populations

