3.3 Study Endpoints

3.3.1 Primary Endpoints

Coprimary Immunogenicity Endpoints

- Difference in anti-CHIKV SNA seroresponse rate (PXVX0317 minus placebo) and associated 95% CI at Day 22.
Success criterion: Lower bound of the two-sided 95% CI on the difference in seroresponse rates between PXVX0317 and placebo groups █ (equivalent to a difference >0 using a two-sided chi-square test).
- Anti-CHIKV SNA GMT and associated 95% CIs at Day 22 for PXVX0317 and placebo.
Success criterion: Significant difference in the IEP across all age groups combined using an ANOVA model with logarithmically transformed anti-CHIKV SNA titers (\log_{10}) as the dependent variable and treatment group and study site as the fixed effects with a two-sided significance level of 0.05.

Note: Seroresponse rate (considered the presumptive seroprotection rate) is defined as the percentage of participants who achieve an anti-CHIK SNA █. See Section 9.6.2 for immunogenicity analysis details and Section 9.4 for success criteria and multiplicity controls.

Safety Endpoints

- Incidence of solicited AEs through Day 8 for PXVX0317 and placebo.
- Incidence of unsolicited AEs through Day 29 for PXVX0317 and placebo.
- Incidence of SAEs, MAAEs, and AESI through Day 183 for PXVX0317 and placebo.

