3.4.2 Treatment Assignment/Randomization

Participant eligibility will be confirmed and documented by the investigator immediately prior to randomization of each participant on Day 1. Study staff will indicate on a randomization eCRF within the EDC system that they want to generate a randomization number for the participant. When they agree to proceed, a randomization number will be generated from the EDC randomization module but hidden from study staff. The EDC randomization module will match the randomization number to an IP kit available at the site

and inform the study staff of the assigned kit. Study staff will use the appropriate kit for planned administration to the participant.

Participants will be considered enrolled once a randomization number has been assigned within the EDC system. Participants will be stratified by age subgroups (65 to <75 years and ≥75 years of age), with a target of 25% enrollment of participants ≥75 years of age.

Participants will be randomized to PXVX0317 or placebo in a 1:1 ratio.

The study will be conducted as a double-blind study through Day 183 End of Study Visit. Neither participants nor clinical site personnel, including the PI, nor the sponsor will know participants' individual treatment assignments until all participants have either prematurely discontinued or completed their participation in the study through the Day 183 End of Study Visit and the database has been cleaned and locked.

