9.4 Multiplicity Controls

9.4.1 Coprimary Immunogenicity Endpoints

The familywise error rate will be fixed at a two-sided alpha of 0.05 by the requirement that both coprimary immunogenicity endpoints must be met for a successful outcome:

1. Day 22 seroresponse in the IEP across all age groups combined, including superiority to placebo and the success criterion of the lower bound of the two-sided Newcombe hybrid score method 95% CI on the difference in seroresponse rates between PXVX0317 and placebo [REDACTED].
2. Day 22 GMTs significantly different between PXVX0317 and placebo in the IEP across both age groups combined using an ANOVA model with logarithmically transformed anti-CHIKV SNA titers (\log_{10}) as the dependent variable and treatment group and study site as the fixed effects with a two-sided significance level of 0.05.

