9.6.2.1.2 Day 22 Geometric Mean Titer Analysis

In addition, Day 22 GMTs will be compared between PXVX0317 and placebo treatment groups and will be analyzed via a linear model based on an alpha=0.05. The primary model is an ANOVA, with logarithmically transformed anti-CHIKV SNA titers (\log_{10}) as the dependent variable and treatment group and study site as the fixed effects in the model. The adjusted least square means and their 95% CIs calculated based on the ANOVA will be back transformed and reported as the group GMT values. All tests will be carried out at a two-sided significance level of 0.05 and no adjustment for multiplicity will be applied.

The primary comparison will be in the IEP across both age groups combined. Tests will be repeated in the mITT population as a measure of robustness, along with tests for each population in the separate age strata. No multiplicity adjustment will be made for the analysis of the separate age strata as the primary population will be the combined age groups.

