### 2.2 Study Design and Conduct

This is a phase 3, randomized, double-blind, placebo-controlled, parallel-group study with two treatment groups. This multicenter study is conducted in the US with up to 10 sites. At least 400 enrolled healthy US participants  $\geq 65$  years of age and older are enrolled, stratified in two age subgroups ( $\geq 65$  to  $< 75$  and  $\geq 75$  years of age) with a target of 25% enrollment of participants  $\geq 75$  years of age. Participants are randomized in a 1:1 ratio to receive either a

single intramuscular (IM) dose of PXVX0317 or placebo at Day 1. With 400 participants enrolled, the treatment group totals are estimated as follows:

- Group 1- PXVX0317: n=200
- Group 2- Placebo: n=200

The per participant estimated total study duration is 212 days (including screening). The screening window is no greater than 30 days prior to Day 1 (randomization and administration of investigational product [IP]). Screening assessments include informed consent, review of eligibility criteria, medical history, prior and concomitant medications, demography, physical examination including height and weight for body mass index calculation, vital signs, urine toxicology screening per investigator's discretion, and viral markers for hepatitis B surface antigen (HBsAg), hepatitis C (HCV) and human immune deficiency virus 1 and 2 (HIV-1/HIV-2).

[figure not shown]
Prior to IP administration on Day 1 (baseline), eligibility, medical history and concomitant medications are reviewed, and a baseline anti-CHIKV SNA sample is drawn. Vital signs including blood pressure, heart rate, respiratory rate and temperature are taken on Day 1 before and after IP administration. Directed physical examinations are performed if indicated at Days 1, 15, 22 and Day 183 End of Study Visit (EOS). The immune response to PXVX0317 is measured by anti-CHIKV SNA at Day 15, Day 22 (coprimary endpoints are at Day 22) and Day 183 EOS (or at Early Discontinuation/ Withdrawal). No safety laboratory samples are collected as part of the study.

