### 6.1.2 Geometric Mean Titers and Geometric Mean Fold Increase

The superiority of PXVX0317 vaccine immunogenicity over that of placebo is explored further by comparing Day 22 GMTs derived from a linear model with a one-sided alpha=0.025. The primary model is an analysis of variance (ANOVA), with  $\log_{10}$ -transformed anti-CHIKV SNA titers ( $\log_{10}$ ) as the dependent variable and treatment group and study site as the fixed effects in the model. No interaction term is used. The adjusted least square means and their 95% CIs calculated based on the ANOVA are back transformed and reported as the group GMT values. No adjustment for multiplicity is applied. See Section 6.4 for statistical hypothesis, Section 6.9 for multiplicity considerations, and Section 8.4.1.2 for analysis outputs. Identical methods are used for treatment group comparison of GMTs at Days 15 and 183.

Geometric mean fold increase (GMFI) from baseline (Day 1) to Days 15, 22 and 183 is calculated using the difference from Day 1 in  $\log_{10}$ -transformed titers as the dependent variable in the ANOVA model. The adjusted least square means and their 95% CIs calculated based on the ANOVA are back transformed and reported as the group GMFI values. The median, minimum and maximum titers and fold-increases are based on the non-transformed scale.

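### The pooled Day 22 GMT model fits site but omits age stratum, the only named randomisation factor, so the SE of the between-arm contrast is slightly too large if titer differs by age

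*SAP*

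**What the plan says.** Protocol 3.4.2 sets the design: "Participants will be stratified by age subgroups (65 to <75 years and ≥75 years of age"), with 1:1 allocation and a target of 25% in the older stratum. SAP 2.2 repeats that participants are "stratified in two age subgroups", and SAP 2.3.2 defines stratification errors, so the factor operates at randomisation. Site is not named as a stratification factor.

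The model is the same wherever it is described. The protocol synopsis has "treatment group and study site as fixed effects", and Protocol 9.6.2.1.2 has "treatment group and study site as the fixed effects in the model". SAP 6.1.2 adds that interactions are excluded: "treatment group and study site as the fixed effects in the model. No interaction term is used". SAP 6.6 rules out anything more: "Beyond the inclusion of site in the immunogenicity ANOVA models described in Section 6.1, no further adjustment for covariates is performed".

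Success is judged on the pooled strata. Protocol 9.4.1 requires "Day 22 GMTs significantly different between PXVX0317 and placebo in the IEP across both age groups combined using an ANOVA model", and SAP 6.9.1 confirms the pooled analysis as primary. Age enters only through repeats of the analysis within each stratum.

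**The concern.** Stratified randomisation balances age across the arms, so a difference in titer between the strata adds almost nothing to the true variability of the between-arm contrast. A model without age still counts that difference as residual noise. Its SE therefore takes no credit for the balance the design provides. Site, which is not a named stratification factor, is fitted; age is not, and neither document gives a reason. The by-stratum repeats do not help, because they play no part in the pooled success test.

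At stake is the accuracy of the SE, interval and p-value for a coprimary contrast. The seroresponse endpoint is not affected, and the point does not concern the arm-level GMT intervals.

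**Working it through.** **The plan's own figures.** The documents give no SD, SE or power for the GMT endpoint. The only power statement (Protocol 9.1, SAP 4.1) is for seroresponse: above 99.9% with 180 per arm. It reproduces: even a vaccine rate of 25% against 5% gives 99.98%. The enrolment figure also agrees: 180/(1 − 0.10) = 200 per arm.

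**Inputs from the documents.** 180 evaluable per arm; 25% aged ≥75; treatment and site as the only model terms; IEP seronegative at baseline (SAP 5.3); values below LLOQ set to LLOQ/2 (SAP 6.3).

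**Assumptions.** Within-stratum SD 0.4 or 0.5 log10; age gap d of 0.2 or 0.3 log10 in the vaccine arm only, since placebo titers in seronegative participants should sit near LLOQ/2; age balanced across arms.

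**Formulas.** Let w = SD² and b = 0.75 × 0.25 × d², so b = 0.0075 at d = 0.2 and 0.016875 at d = 0.3. The contrast SE is sqrt(2V/n), with V as follows.

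| | Planned model | With additive age | True |
|---|---|---|---|
| Equal SDs in both arms | w + b/2 | w + b/4 | w |
| Placebo with no spread | w/2 + b/2 | w/2 + b/4 | w/2 |

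The additive term leaves b/4 because it fits one common age effect, d/2, to two arms whose real effects are d and 0.

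**Worked case: placebo with no spread, SD 0.4, d = 0.3.** Planned V = 0.08 + 0.0084375 = 0.0884375; with age V = 0.08 + 0.00421875 = 0.08421875; true V = 0.08.
- Planned excess: sqrt(0.0884375/0.08) − 1 = 5.14%.
- Excess with age: sqrt(0.08421875/0.08) − 1 = 2.60%.
- Reduction in model SE: 1 − sqrt(0.08421875/0.0884375) = 2.41%.

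**All cases.**

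| Placebo spread | SD | d | Planned excess | Excess with age | Reduction in model SE |
|---|---|---|---|---|---|
| Same as vaccine | 0.4 | 0.2 | 1.17% | 0.58% | 0.57% |
| Same as vaccine | 0.4 | 0.3 | 2.60% | 1.31% | 1.26% |
| Same as vaccine | 0.5 | 0.2 | 0.75% | 0.37% | 0.37% |
| Same as vaccine | 0.5 | 0.3 | 1.67% | 0.84% | 0.82% |
| None | 0.4 | 0.2 | 2.32% | 1.17% | 1.13% |
| None | 0.4 | 0.3 | 5.14% | 2.60% | 2.41% |
| None | 0.5 | 0.2 | 1.49% | 0.75% | 0.73% |
| None | 0.5 | 0.3 | 3.32% | 1.67% | 1.59% |

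At d = 0.1 the reduction is 0.09–0.29%; at d = 0 it is zero.

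**Simulation of the contrast.** 8,000 trials were simulated with 135/45 by age per arm and ten sites with assumed shares of 20, 16, 14, 12, 10, 8, 7, 6, 4 and 3%. In the worked case the mean model SE was 0.0317 planned and 0.0309 with age, and the empirical SD of the estimate was 0.0304 under both. Over all cases, 95% interval coverage was 94.9–96.0% planned and 94.8–95.4% with age (simulation error about 0.2 point).

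**Arm-level intervals.** With placebo at LLOQ/2, the common ANOVA variance makes the vaccine-arm interval too narrow whether or not age is fitted. Planned coverage was 86.0–87.2% with equal site weights and 84.1–85.2% with enrolment weights. At the same site weights, the age term lowered it by a further 0.1–1.0 point. Arm-specific variances with stratum means gave 94.5–95.6% (4,000 trials).

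**The case against.** The strongest reply is that this is a modelling preference with no practical effect. The two documents agree on the model terms, and the planned test is valid. The empirical SD of the contrast is the same with or without age, so only the printed SE changes.

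The result is also most unlikely to turn on it. With SEs of 0.0317 and 0.0309, significance needs an observed GMT ratio of 10^(1.96 × 0.0317) = 1.154 or 10^(1.96 × 0.0309) = 1.150, so the verdict differs only between those two values. Protocol 1.4.3 reports a GMT of 1712 at 28 days after the single 40 µg dose in younger adults. Take a tenfold lower GMT, assume LLOQ/2 of about 7.5 (the LLOQ is not stated), and assume SD 0.5 in both arms, giving SE = sqrt(2 × 0.25/180) = 0.053. The difference is log10(171.2/7.5) = 1.36, and z is about 26.

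The size of the effect rests wholly on assumptions. Protocol 1.7 raises immunosenescence for adults ≥65 as one group, not for ≥75 against 65 to <75. The remedy slightly narrows vaccine-arm intervals that may already be too narrow, and it needs a formal amendment.

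All of this stands as fact, and it fixes the grade at minor. It does not answer the point itself: a factor the trial randomises by is missing from a coprimary model, and fitting it brings the SE of the contrast closer to its true value using data already collected. The arm-level coverage problem is a separate matter of unequal variances and lends no weight here.

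**Conclusion.** The point holds and is minor. The planned SE of the Day 22 log10 GMT difference is too large by roughly 1–5% under the stated assumptions, and by nothing if titer does not differ by age. The error is conservative. Fitting age does not reduce the true variability of the estimate; it makes the reported SE more accurate, and an additive term recovers only about half the excess when age acts in the vaccine arm alone.

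A gap of the same size in both arms would give a larger excess: 0.4–16.3% for gaps of 0.1–0.4 log10 and vaccine/placebo SD pairs of 0.4/0.1, 0.5/0.1, 0.6/0.2 and 0.5/0.5. That is less plausible with placebo titers near LLOQ/2. Exact age balance in the IEP is an approximation, because about 10% of participants are expected to be non-evaluable.

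**What to change.** Add age stratum, using the corrected stratum that SAP 6.3 already prescribes, as a fixed effect in the pooled GMT model, and in the GMFI model for consistency. Specify observed-margin weights for the least-squares means. Align SAP 6.1.2, 6.4.1 and 6.6 with the protocol synopsis, 3.3.1, 9.4.1 and 9.6.2.1.2.

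Timing is the condition. The change must precede any unblinded Day 22 result, including the group-level preliminary summaries sent to the sponsor under SAP 10.2.1. The documents do not show whether these have been released. If they have, the change should not replace the primary model.

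The costs and downsides should be stated with the change:
- A formal amendment with IRB approval (Protocol 13.2). The rest is SAP wording, one model term and one least-squares-means option. No new data are needed.
- Observed margins also weight sites by enrolment. With the site shares assumed above and site means varying with SD 0.05–0.10 log10, the typical shift is site SD × sqrt(0.027) = 0.0082–0.0164 log10. Both arms' GMTs move by the same factor, 1.019–1.039. With no interaction term, the contrast and its test are unchanged.
- Default equal age weights would be worse: they would lower both arms' GMTs by 0.25 × d/2 = 0.025–0.0375 log10, or 6–8%.
- Arm-level GMT intervals are not improved. If they are to be relied on, they need arm-specific variances.

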## 6.7 Multicenter Study

This study is expected to enroll 400 participants at up to 10 sites in US. Data from all sites will be pooled, but site will be a covariate in the immunogenicity ANOVA models described in Section 6.1.

## 6.8 Subgroup Analyses

Summaries pool both age groups and are repeated separately for each age group. Analyses of the primary immunogenicity and safety endpoints are also summarized by sex, race, and ethnicity group along with treatment group. Summaries by baseline anti-CHIKV SNA serostatus are reported if the baseline (Day 1) seropositive rate is  $\geq 10\%$ .

## 6.9 Multiplicity Adjustment

### 6.9.1 Coprimary Immunogenicity Endpoints

The familywise error rate is fixed at a two-sided alpha of 0.05 by the requirement that both coprimary endpoints must be met for a successful outcome: seroresponse at a titer of ■ (HA1) and GMT (HA2). See Section 6.4 for formal statistical hypotheses.

For each individual coprimary endpoint, the primary time point is Day 22 and the primary analysis population is the IEP. For the seroresponse and GMT endpoints, the primary analysis is for the pooled age strata; no multiplicity adjustment is made for the analysis of the mITT population or of the separate age strata as the primary population is the combined age groups in the IEP.

### 6.9.2 Key Secondary Immunogenicity Endpoints

Seroresponse key secondary immunogenicity endpoints are tested using a prespecified hierarchical strategy to preserve the type I error rate without the need for further multiplicity adjustment. These endpoints are tested formally only if the null hypotheses are rejected for both coprimary endpoints and only until a nonsignificant test is reached. If a nonsignificant test is reached formal testing stops, and the remaining endpoints are reported for information only. The sequential order of the seroresponse rate difference key secondary endpoints (HA3) is Day 15 and Day 183, each for the IEP across both age groups combined. At Days 15 and 183, the endpoint is tested for superiority to placebo using a two-sided chi-square test with alpha=0.05.

1. Day 15 seroresponse at a titer of ■, including superiority to placebo.
2. Day 183 seroresponse at a titer of ■, including superiority to placebo.

After testing the coprimary immunogenicity endpoints and, if both met, the hierarchical key secondary immunogenicity endpoints, no other formal hypothesis testing is performed. The remaining secondary immunogenicity endpoints involving GMTs, GMFI, other titers, the exploratory endpoint, and all safety endpoints are evaluated and reported for information only, thus no further multiplicity adjustment is needed.

## 7 STUDY POPULATION CHARACTERISTICS

### 7.1 Participant Disposition

Participant disposition over the course of the study is summarized for all randomized participants by treatment group, including number and percentages of participants still in the study each scheduled visit, competing the study, and reason for not completing the study. Screen failure reasons are listed by participant. The number and percentage of participants enrolled by site are provided by treatment group for all randomized participants.

Randomization details including site, stratum, date and time of randomization, kit number, randomized treatment group assignment, and actual treatment received including lot number are listed by participant. Participants randomized but not treated, those receiving the wrong treatment, or receiving an incorrect dose are listed. Participants who were randomized despite not meeting entry criteria and those who received an excluded concomitant medication are listed.

### 7.2 Protocol Deviations

Protocol deviations defined in Section 5.2 are categorized as important or not important and evaluated for exclusion of participants from analysis populations. Important protocol deviations are tabulated by category and by treatment group for the randomized population as well as listed by participant.

